6. STUDY DESIGN

6.1. Description of the Study

This is a Phase 1, single-center, prospective, randomized, double-blind study of ascending single doses of CD388 Injection administered SQ to healthy Japanese adult subjects. The goals are to assess safety, tolerability, and PK of CD388.

Subjects will be randomized to receive a single dose of CD388 or placebo administered via SQ injection (treatment assignment is blinded) according to the design in Table 3.

Table 3: Study Design

Number of Subjects (N = 27)				
Cohort: dose	CD388 (n = 21)	Placebo (n = 6)		
Cohort 1: 50 mg	7	2		
Cohort 2: 150 mg	7	2		
Cohort 3: 450 mg	7	2		

Note: A subject may not receive treatment in more than one cohort.

After 50% of Cohort 1 subjects have completed study drug administration and have undergone protocol-specified procedures and assessments for ≥10 days, the Principal Investigator (PI) and Sponsor will review blinded safety data: AEs (including systemic reactogenicity/injection site reactions, hypersensitivity reactions, and adverse events of special interest [AESIs]), vital signs, 12-lead ECGs, and clinical laboratory results (hematology, coagulation, serum chemistry, urinalysis) to determine the safety and tolerability of the study drug. The incidence and severity of AEs, and any adverse changes in vital signs, clinical laboratory findings, and ECGs will be considered when determining safety and tolerability of study drug. If the dose is determined to be safe and well tolerated ≥10 days after dosing, Cohort 2 will be enrolled. Enrollment of the remaining 50% of Cohort 1 will continue while the safety data of the first 50% of Cohort 1 is being reviewed. Similar processes will be followed for dose escalation from Cohort 2 to Cohort 3.

The Schedule of Events is presented in Table 1. All subjects will be admitted to the clinical research unit (CRU) for observation and safety assessments from Day -1 (check-in) to Day 14. Subjects will be monitored for AEs (including systemic reactogenicity/injection site reactions, hypersensitivity reactions, and AESIs) and SAEs throughout the study until the final study visit after dosing. Safety will also be assessed by physical examinations, ECGs, vital signs measurements, and laboratory evaluations (hematology, coagulation, serum chemistry, urinalysis) at various time points during and after the CRU stay. Concomitant medication use will be recorded throughout the study.

Blood samples for PK and ADA assessments will be collected throughout the study. To maintain the blind, samples will be collected from all subjects; however, only samples from the CD388 Injection group will be analyzed (using validated assays) by an unblinded central bioanalytical laboratory. Additional blood samples will be collected for pharmacogenomics and exploratory biomarker evaluation.

Respiratory tract infection (RTI) surveillance will be conducted during the outpatient phase of the study from CRU discharge through the Day 120/165 outpatient visit or a lab-confirmed influenza infection, whichever occurs first. Subjects will be provided nasal/throat swab kits (for detection of influenza infection or other respiratory pathogen by a multiplexed polymerase chain reaction [PCR] test) and symptom diary cards.

If 3 or more RTI symptoms listed in the table below occur (at least one must be a respiratory symptom), subjects will contact study staff, then collect nasal/throat swab samples (the swabs should take place as soon as possible after the start of symptoms, ideally within 48 hours, but no later than 5 days). Subjects will complete symptom diary cards every 7 days to capture the worst grade of symptoms that occurred during the previous week. The Investigator/study staff will arrange for prompt shipment of the nasal/throat samples to the testing laboratory. Note: If the reported symptoms are already of a level of severity that urgent care is indicated, the subject should be directed to the appropriate facility to receive this care (e.g., emergency room). Otherwise, symptoms should be treated according to standard of care.

If an influenza infection is confirmed by the testing laboratory before the Day 120/165 outpatient visit, the event should be documented until all symptoms have resolved, including completion of the symptom diary card every 7 days. Thereafter, no further RTI surveillance will be carried out on the subject.

If the nasal/throat swab samples are not confirmed to be influenza by the testing laboratory, diary card completion will continue through the Day 120/165 outpatient visit.

Re	Respiratory Tract Infection (RTI) Symptoms				
•	Runny nose (rhinorrhea)	•	Shortness of breath (dyspnea)		
•	Stuffy nose (nasal congestion)	•	Wheeze		
•	Sore throat	•	Chilliness/feverishness or temperature ≥100°F		
•	Earache	•	Headache		
•	Cough	•	Body ache		
•	Productive phlegm/sputum				

As part of the surveillance, subjects will be questioned during all outpatient site visits for RTI symptoms. If the interval to the next outpatient site visit exceeds 15 days, subjects will be contacted by the Investigator/study staff every 2 weeks to query for RTI symptoms. Subjects should be reminded to contact the Investigator/study staff if RTI symptoms occur, and to collect the nasal/throat swab samples and complete the symptom diary cards every 7 days.

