1.1. Schedule of Events

Table 1: Schedule of Events

	Screening		Clinica	al Resea	Clinical Research Unit (CRU) Inpatient Stay	(CRU) I	npatient	Stay			Outpa	Outpatient CRU Visits	tU Visit	20
Day (Window)	-28 to -2	-1	1	2	3–6	L	6	11	14	30 (±3)	45 (±3)	(5±)	90 (±7)	120/165 a (±14)
Informed consent	X													
Inclusion/Exclusion criteria	X	X												
Medical history/demographics	X													
Complete physical with vital signs (BP, RR, HR, oral temperature, height, weight, BMI)	X													
Targeted physical with vital signs (BP, RR, HR, oral temperature, weight ^b)		×	×°	×	X	X			×	X	X	×	×	×
Safety ECG ^d	X	X	X			X			×	X				X
Laboratory evaluations (CBC with platelets, coagulation, serum chemistry, lipids, urinalysis)	X	X		X	X e	X			X	X	X	X	X	×
Virology screening (HBV, HCV, HIV)	X													
Virology screening (SARS-CoV-2)		×												
Serum/urine pregnancy test f	X	X								X		×	X	X
FSH (if applicable to confirm postmenopausal status)	X													
Drug/alcohol screen 8	X	X												
Randomization			X											
Dosing of study drug			X											
Reactogenicity/injection site inspection h			X	X	X									
PK sample collection i			X	X	X	X	X	X	X	X	X	X	X	X
Pharmacogenomics blood sample ^j			predose											
Exploratory biomarker samples			predose		X e									
Anti-drug antibodies			predose						X	X	X	X	X	X
Nasopharyngeal swab collection ^k			predose	X	X	X	X	X	X	X				
Assess and record AEs ¹	→													↑
Concomitant medications/procedures review m	\													↑

[figure not shown]
research unit; DAR = drug-antibody ratio; ECG = electrocardiogram; FSH = folliele-stimulating hormone; HBV = hepatitis B virus; HCV = hepatitis C virus; HIV = human Abbreviations: AEs = adverse events; BMI = body mass index; BP = blood pressure, CBC = complete blood count; COVID-19 = coronavirus disease 2019; CRU = clinical immunodeficiency virus; HR = heart rate; hr = hour; ICF = informed consent form; PK = pharmacokinetic; RR = respiration rate; SARS-CoV-2 = severe acute respiratory syndrome coronavirus 2.

Schedule of Events (continued)

- The timing of this visit is Day 120 for Cohort 1 and Day 165 for Cohorts 2 and 3. For subjects who discontinue study early, the Day 120/165 procedures should be performed.
- b. Weight should be measured at each of the outpatient visits (Days 30, 45, 60, 90, 120/165).

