11.2. Adverse Events

Adverse events will be collected for all subjects from the time of signing the ICF through the final study visit. The Investigator will assess all AEs and SAEs and will record the following information on the appropriate eCRF page:

- Date of onset
- Resolution status, and date of resolution or stabilization if achieved
- Seriousness
- Severity
- Causal relationship to study drug
- Action taken with study medication

Medically indicated laboratory tests (emergency or unscheduled tests) should be conducted at the local laboratory. The Investigator should employ best medical judgment in determining how to manage AEs and SAEs. Any questions regarding AE or SAE management should be directed to the Medical Monitor.

The Sponsor is responsible for:

- Confirming the seriousness assessment of all reported AEs and SAEs
- Confirming the causal relationship between reported AEs/SAEs and the investigational product
- Assessment of SAEs for expectedness

The Sponsor will continuously assess the safety of the investigational product throughout the study.

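### No general adverse event or medication query is specified between Day 90 and Day 165 in Cohorts 2 and 3, although staff already contact subjects every two weeks about RTI symptoms

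*Protocol*

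**What the plan says.** Section 5 makes the incidence and severity of treatment-emergent adverse events the primary endpoint, and section 12.3 counts such events through the final study visit. Collection is meant to be continuous. Section 11.2 states: "Adverse events will be collected for all subjects from the time of signing the ICF through the final study visit". Section 6.1 likewise has subjects monitored for adverse events and "SAEs throughout the study until the final study visit after dosing". Section 9.10 records concomitant medications over the same span.

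After discharge on Day 14, the visits in Table 1 are Days 30, 45, 60, 90 and 120/165. The footnote on the last one reads: "The timing of this visit is Day 120 for Cohort 1 and Day 165 for Cohorts 2 and 3".

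Between visits, section 6.1 provides a contact as part of RTI surveillance. "If the interval to the next outpatient site visit exceeds 15 days", then "subjects will be contacted by the Investigator/study staff every 2 weeks to query for RTI symptoms". Its other stated content is also about RTI: "Subjects should be reminded to contact the Investigator/study staff if RTI symptoms occur", together with reminders about swabs and diary cards. The contact has no row in Table 1. After a laboratory-confirmed influenza has been followed to resolution, section 6.1 says: "Thereafter, no further RTI surveillance will be carried out on the subject".

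**The concern.** RTI symptoms serve an exploratory objective, but they are asked about every two weeks and recorded weekly in a diary. The other clinical events that make up the primary endpoint have no specified prompt for 75 days in the two higher-dose cohorts.

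Three things are at stake.

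- **Completeness.** Minor events that nobody asks about are easily forgotten by the final visit, as are medicines taken in the interval. Section 8.5 restricts most medicines until after the final visit, so their use is of interest.
- **Comparability.** Section 12 summarizes data by dose level, but the last unprompted interval is 30 days at 50 mg and 75 days at 150 mg and 450 mg.
- **SAE awareness.** The 24-hour reporting time in section 11.3.1 runs from the site's knowledge of the event. An SAE that nobody asks about and the subject does not volunteer could stay unknown until the final visit.

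**Working it through.** The protocol gives no figure for this interval, so there is none to reproduce. The check is date arithmetic on Table 1.

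**Inputs.** Discharge on Day 14. Visits on Days 30 (±3), 45 (±3), 60 (±5), 90 (±7), then 120 for Cohort 1 or 165 for Cohorts 2 and 3 (±14). Contacts every 14 days when the interval to the next visit exceeds 15 days (section 6.1). Each cohort has 7 subjects on CD388 and 2 on placebo (Table 3).

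**Formulas.** For consecutive visits on days a and b with windows w_a and w_b:

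- nominal gap = b − a
- shortest gap = (b − w_b) − (a + w_a)
- longest gap = (b + w_b) − (a − w_a)

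| Interval | Nominal (days) | Shortest | Longest | Contacts inside nominal gap |
|---|---|---|---|---|
| Day 14 to 30 | 16 | 13 | 19 | 1 |
| Day 30 to 45 | 15 | 9 | 21 | 0 |
| Day 45 to 60 | 15 | 7 | 23 | 0 |
| Day 60 to 90 | 30 | 18 | 42 | 2 |
| Day 90 to 120 (Cohort 1) | 30 | 9 | 51 | 2 |
| Day 90 to 165 (Cohorts 2 and 3) | 75 | 54 | 96 | 5 |

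**The last gap, like for like.**

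- Cohorts 2 and 3: nominal 165 − 90 = 75; shortest 151 − 97 = 54; longest 179 − 83 = 96.
- Cohort 1: nominal 120 − 90 = 30; shortest 106 − 97 = 9; longest 134 − 83 = 51.

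**Extent.** 75/165 is about 45% of the follow-up in Cohorts 2 and 3. They hold 2 × 9 = 18 of 27 subjects, of whom 2 × 7 = 14 of 21 receive CD388 and 4 receive placebo.

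**Contacts already planned.** Steps of 14 days from Day 90 give Days 104, 118, 132, 146 and 160, so five contacts (three in a 54-day gap, six in a 96-day gap).

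**After the change.** With an adverse event question at each contact, the longest prompted interval on the nominal schedule is 14 days in gaps that contain contacts. It is 15 days in the two gaps that do not exceed the 15-day trigger. From Day 160 to Day 165 is 5 days.

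**Which events rest on recall.** The remaining text narrows the group:

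- Any rash calls for immediate contact and an unscheduled visit (Appendix 4).
- Pregnancy must be reported at once (section 11.8).
- Headache, body ache and feverishness are on the RTI symptom list that the weekly diary serves (section 6.1).
- Laboratory, ECG and vital-sign results are measured at visits and do not depend on recall.

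What remains is symptomatic, non-RTI, non-rash events, and medication use.

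**The case against.** Section 6.1 states what the contact is for and contains no word that restricts it. Since adverse event collection is continuous under section 11.2, an event volunteered during a call has to be recorded. Site or case report form instructions that are not shown may already tell staff to ask. This stands, and it rules out the reading that the contacts exclude other events or that every other adverse event depends on 75 days of recall. It does not supply a prompt: the protocol gives a method of asking about RTI symptoms between visits and none for anything else.

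A reader might also infer that the higher doses will look safer because their last gap is longer. The documents do not support that direction. Cohorts 2 and 3 are followed for 165 − 120 = 45 more days, which tends to raise their cumulative incidence. Placebo subjects within each cohort follow the same schedule under blinding, so the within-cohort comparison is affected equally. Nor should 96 days be set against 30, because that compares a windowed maximum with a nominal value.

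Finally, no stated decision rests on this period. Escalation uses data from at least 10 days after dosing (section 6.1), the halting rules look at 28 days (section 7.6), and there is no formal hypothesis testing (section 12). That limits the consequence. It does not remove the point, because the protocol itself chose to count events to Day 165.

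**Conclusion.** The point holds as a moderate weakness in how late events are ascertained. It is neither a contradiction nor a numerical error. In Cohorts 2 and 3, the protocol specifies no general adverse event or medication query for 75 days (54 to 96 with windows), against 30 days (9 to 51) for Cohort 1's last gap. Late treatment-emergent events are therefore under-prompted, and Cohort 1 differs from Cohorts 2 and 3 in this respect. The net direction of any bias across doses is unknown. For a subject with confirmed influenza, even the RTI contact ends.

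This rests on reading section 6.1 as the full specification of the contact, and on visits taking place within the Table 1 windows. If unseen site instructions already include a general question at these calls, what remains is to write that into the protocol.

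**What to change.** In section 6.1 and the matching synopsis text, widen the stated purpose of the two-weekly contact to cover adverse events and concomitant medications as well as RTI symptoms. State that the contact continues for adverse events to the final visit after RTI surveillance has ended for a confirmed influenza. Add the contact as a row in Table 1.

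The cost is small: one or two more questions on calls already planned, and no new visits. Subjects with confirmed influenza would receive a few calls that are not now planned, and slightly more mild adverse events would be recorded.

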6.2. Criteria for Evaluation

6.2.1. Safety and Tolerability of Study Drug

Safety and tolerability will be assessed by monitoring AEs (including systemic reactogenicity/injection site reactions, hypersensitivity reactions, and AESIs), vital signs, 12-lead ECGs, clinical laboratory results (hematology, coagulation, serum chemistry, urinalysis), and concomitant medication usage throughout the study.

See Section 6.1 for details regarding cohort/dose level enrollment timing and assessment of safety and tolerability for dose escalation decision.

If a dose level is considered not safe or well tolerated, the study drug assignment for the subject(s) with the safety issue may be unblinded. The Sponsor may also independently decide to unblind the entire cohort for safety concerns or terminate enrollment for any reason.

If any subject develops a Grade ≥2 AE or an SAE of any grade that is deemed related to the study drug, the mechanism of the AE may be assessed (i.e., cytokine level, complement activation, immunoglobulin G [IgG] subtypes, immunoglobulin E [IgE], T-cell/B-cell/monocyte and basophil activation as assessed by flow cytometry, ADA development, and immune complex formation) at Sponsor and Investigator discretion, and the study dose may be modified for the remainder of the study.

6.2.2. Pharmacokinetics/Anti-drug Antibodies

Pharmacokinetics will be determined by analyzing plasma samples for concentration of CD388 obtained from subjects who receive CD388 Injection in each cohort at various time points after administration of study drug. Anti-drug antibodies will also be measured at selected time points by a validated ELISA method.

6.2.3. Pharmacogenomics

A mandatory pharmacogenomic (DNA) blood sample will be collected once, preferably on Day 1 (collection at another time point is permitted if necessary) to allow for genetic research to help understand the characteristics of CD388. Genetic analysis will be conducted if it is hypothesized that doing so may aid in exploring genetic markers which could explain differences in safety, immunogenicity, or clinical response among subjects. Host DNA assessment will be limited to research related to CD388, including the development of tests/assays related to CD388 and flu-like disease.

Analyses of host DNA may be conducted at the Sponsor's discretion and reported separately from the study report.

6.2.4. Exploratory Biomarkers

Blood samples will be collected to allow for the exploration of biomarkers on the assumption that these markers could play a role in the response (safety, reactogenicity, immunogenicity) to CD388.

These samples and remaining material from other samples may be used for further assay optimization/qualification, biomarkers, or further exploratory analyses. Samples will only be used for research related to influenza virus infection, flu-like disease, and safety, reactogenicity, and immunogenicity of CD388, including the development of tests/assays related to CD388 and influenza.

Analyses of biomarkers may be conducted at the Sponsor's discretion and reported separately from the study report.

6.3. Number of Subjects

A total of 27 healthy volunteers will be enrolled in this study in 3 cohorts: 9 of the 27 subjects will be enrolled in the first cohort and randomized in a 7:2 ratio to receive either 50 mg CD388 SQ injection or matching placebo injection; the remaining subjects will be enrolled in the second

and third cohorts (9 subjects each) and randomized in a 7:2 ratio to receive either 150 mg (Cohort 2) or 450 mg (Cohort 3) CD388 SQ injection or matching placebo injection.

6.4. Measures Taken to Minimize Bias

Study drug assignment (CD388 Injection or placebo) will be blinded to all blinded clinical site and Sponsor study team until at least after the final subject in a cohort has completed the Day 90 visit. Unblinded personnel include the site pharmacist (or pharmacist designee) preparing the injections, the unblinded pharmacy monitor (to ensure study drug accountability and assignment throughout the trial), and the Sponsor's unblinded team.

6.5. Expected Duration of Subject Participation

A single dose of study drug will be administered SQ on Day 1. Study participation will require up to 28 days for screening procedures, and approximately 120/165 days for dosing and follow-up (check-in to the CRU on Day -1; CRU inpatient stay for study drug administration, observation, and assessments and procedures for 15 days [Days -1 to Day 14]; and 5 CRU outpatient visits for additional assessments and procedures).

6.6. Method of Treatment Assignment and Blinding

After informed consent has been obtained, subjects will be screened for study eligibility before randomization.

Within each dose level (Cohorts 1, 2, and 3), subjects will be randomized to receive a single dose of CD388 Injection or saline placebo (treatment assignment is blinded). The study site's pharmacist (or pharmacist designee) will obtain a computer-generated study drug assignment. A subject is considered randomized when a randomization transaction is appropriately recorded.

Unless a formal interim analysis is conducted after all subjects have completed the Day 90 visit, all blinded study personnel (including the Sponsor, Investigator, and site personnel directly involved in study conduct) and subjects will remain blinded to study drug assignment until the study is completed and the final database is locked with the exception of the unblinded pharmacy personnel, pharmacy monitor, and unblinded Sponsor personnel (such as Data Review Committee, clinical supply manager, PK lead, and quality manager) who may be unblinded to study medication at any time during study conduct. The pharmacy monitor will monitor study drug preparation and accountability during the study and cases in which unblinding is required due to a safety or tolerability issue. To maintain study blinding, study drug preparation will be performed by an unblinded site pharmacist (or qualified unblinded personnel at the study site not involved with study procedures or evaluations). Any unblinding related to an interim analysis will be documented in the blinding plan.

Instructions for study drug preparation and dosing are outlined in the Pharmacy Manual provided separately to the site. In the event of a medical emergency requiring the Investigator to know the identity of the study drug, the Investigator will follow the procedures outlined in Section 8.4.

6.7. Data Review Committee

A Sponsor Data Review Committee, consisting of representatives of the Sponsor not involved in day-to-day management of the study, may be established to review unblinded data to allow

strategic development decisions within and across development programs. The procedures of the Data Review Committee will be documented in a charter.

7. SELECTION, DISCONTINUATION, AND WITHDRAWAL OF SUBJECTS

7.1. Subject Inclusion Criteria

Subjects must meet ALL the following inclusion criteria:

- 1. Must be of Japanese descent with Japanese parents and grandparents, as determined by subject's verbal report.
- 2. Willing and able to provide written informed consent.
- 3. Males and females 18 to 65 years of age, inclusive.
- 4. A female subject must meet one of the following criteria:
 - a. If of childbearing potential agrees to use a highly effective, preferably user-independent method of contraception (failure rate of <1% per year when used consistently and correctly) for at least 30 days prior to screening and agrees to remain on a highly effective method until 7 months after last dose of study medication. Examples of highly-effective methods of contraception are located in Appendix 1.
 - b. If a female of non-childbearing potential should be surgically sterile (i.e., has undergone complete hysterectomy, bilateral oophorectomy, or tubal ligation/occlusion without reversal surgery) or in a menopausal state (at least 1 year without menses), as confirmed by follicle-stimulating hormone (FSH) levels (≥40 mIU/mL).
- 5. A woman of childbearing potential must have a negative highly sensitive serum pregnancy test (β-human chorionic gonadotropin) at screening and a negative urine pregnancy test on Day -1 before the first dose of study drug.
- 6. A woman must agree not to donate eggs (ova, oocytes) for the purposes of assisted reproduction during the study and for a period of at least 7 months after study drug administration.
- 7. A male subject that engages in sexual activity that has the risk of pregnancy must agree to use a double barrier method (e.g., condom and spermicide) and agree not to donate sperm during the study and for at least 7 months after the last dose of the study medication.
- 8. Good health and without signs or symptoms of current illness.
- 9. Normal clinical examination, including:
 - a. No physical examination findings that an Investigator determines would interfere with interpretation of study results.
 - b. Screening ECG without clinically significant abnormalities (see Appendix 2).
 - c. Creatinine clearance (CrCL) ≥80 mL/min as calculated using the Cockcroft-Gault equation:

$$CrCL = \frac{(140 - age) \times (weight in kg)}{72 \times (serum creatinine in mg/dL)} \times (0.85 if female)$$

- d. Negative urine screen for drugs of abuse and alcohol at screening and Day -1.
- 10. Body weight ≥50 kg and body mass index between 18.0 and 30.0 kg/m², inclusive, using the following equation:

$$BMI = \frac{(weight \ in \ kg)}{(height \ in \ meters)^2}$$

- 11. Willing to refrain from strenuous physical activity that could cause muscle aches or injury, including contact sports, at any time from screening through 30 days after any dose of study drug.
- 12. Subject has adequate venous access for blood collection.

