Relevant eCRF pages can be appended to communicate information relevant to the SAE, including study drug administration details, medical history, concomitant medications, relevant laboratory test results, and subject outcome information. The SAER should be emailed within 24 hours with as much of the above information as available at the time. The following minimum information is required for reporting an SAE: subject identification, Investigator contact information, an AE with a serious outcome, and the Investigator's assessment of causal relationship to study drug. Serious adverse events are to be reported immediately and under no circumstance should this reporting time exceed 24 hours following knowledge of the SAE. Supplemental information may be transmitted using a follow-up report and should not delay the initial report. The Sponsor may contact the investigational site to solicit additional information or follow up on the event.

The Investigator must take all therapeutic measures necessary for resolution of the SAE. Any medications or procedures necessary for treatment of the SAE must be recorded on the appropriate pages of the subject's eCRF.

If the Investigator becomes aware of any SAEs that occur after the study period that are believed to be causally related to use of the investigational product, they should notify the Sponsor immediately.

The Sponsor will report all suspected unexpected serious adverse reactions (SUSARs) within the required regulatory timeframes to all applicable regulatory authorities and to Investigators as required.

All SAEs that do not meet expedited reporting requirements will be summarized in the Development Safety Update Report (DSUR) and reported annually by the Sponsor as required.

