11.8. Risks for Women of Childbearing Potential or During Pregnancy

The risks of CD388 Injection in pregnant or lactating/nursing women are unknown. Pregnant or nursing female subjects are excluded from this study.

Subjects must be instructed to inform the Investigator immediately if they or their partner becomes pregnant during the study. In the case of a partner pregnancy, partner informed consent must be obtained prior to collecting information related to the pregnancy and to allow the Investigator to follow them for the outcome of the pregnancy. In the event of a confirmed pregnancy, the following actions should be taken:

- The pregnancy should be reported to the Sponsor within 24 hours of the subject notifying the Investigator using the applicable Pregnancy Report Form.
- The Investigator should counsel female subjects regarding the possible effects of CD388 Injection exposure on the fetus and the need to inform the study site of the outcome of the pregnancy.
- The subject or subject's partner, if consented, should be monitored until the postnatal day 28 or until termination of the pregnancy. The outcome should be reported using the Pregnancy Outcome or Abnormal Pregnancy Outcome form.

Pregnancy is not an AE, in and of itself. However, any pregnancy complication or elective termination of a pregnancy for medical reasons will be recorded as an AE or SAE. A spontaneous abortion is always considered an SAE and will be reported as described in the AE and SAE sections. Furthermore, any SAE occurring as an adverse pregnancy outcome post-study must be reported to the Medical Monitor.

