20. APPENDICES

APPENDIX 1. ACCEPTABLE METHODS OF CONTRACEPTION

An acceptable method of contraception includes one of the following:

- Abstinence from heterosexual intercourse
- Hormonal contraceptives (birth control pills, injectable/implant/insertable hormonal birth control products, transdermal patch)
- Intrauterine device (with or without hormones)
- A double barrier method (e.g., condom and spermicide)

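### Inclusion 7 bans sperm donation only for men whose sexual activity risks pregnancy; the ban should cover every male subject

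*Protocol*

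**What the plan says.** Inclusion 7 in Protocol Section 7.1 is a single sentence. It begins "A male subject that engages in sexual activity that has the risk of pregnancy must agree to use a double barrier method", and its second half requires the same man to "agree not to donate sperm during the study and for at least 7 months after the last dose of the study medication". The Synopsis carries the criterion in the same form, so neither place corrects the other.

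Inclusion 6, immediately before it, deals with the corresponding matter for women: "A woman must agree not to donate eggs (ova, oocytes) for the purposes of assisted reproduction during the study", and for at least 7 months after study drug. It contains no condition on sexual activity or childbearing potential.

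Section 11.8 covers pregnancies that do occur. It says "Subjects must be instructed to inform the Investigator immediately if they or their partner becomes pregnant during the study", and that the subject or a consenting partner "should be monitored until the postnatal day 28 or until termination of the pregnancy". It describes the risks of CD388 in pregnant or nursing women as unknown.

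**The concern.** The sponsor decided that sperm donation should be controlled for at least 7 months after dosing. A restriction of that kind should follow exposure to the drug. In inclusion 7 it follows the man's sexual activity instead, which has no bearing on whether he donates. Men outside the condition may receive the same dose, yet the criterion asks nothing of them about donation.

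What is at stake is a gap in a safeguard that the protocol itself chose to impose. A site that applies the criterion literally could enrol such a man, obtain no undertaking from him, and remain fully compliant.

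**Working it through.** No arithmetic applies. The check is a comparison of texts.

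1. **Structure of inclusion 7.** There is one grammatical subject, a male whose sexual activity carries a pregnancy risk. It has two obligations: to agree to a double barrier method, and to agree not to donate sperm. The second has no subject of its own, so it inherits the condition.

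2. **Does the condition fit each obligation?** For the barrier method it does, since a man with no such activity has no use for one. For donation it does not, since donation can take place without that activity.

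3. **Case by case.**

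| Male subject | Barrier method required | Donation ban stated |
|---|---|---|
| Sexual activity risks pregnancy | Yes | Yes |
| No such activity (abstinent, or partners cannot become pregnant) | No, appropriately | No |

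The lower right cell is the fault.

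4. **Comparison with the female criteria.** Inclusion 5 is expressly limited to women of childbearing potential. Inclusion 6 is not: it binds any woman, including one who qualifies as of non-childbearing potential under inclusion 4b. So the protocol narrows a criterion where narrowing is intended and leaves the egg-donation ban general. It offers no reason for treating sperm donation differently.

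5. **Is the gap closed elsewhere?** Sperm donation appears only in inclusion 7, in Section 7.1 and in the Synopsis. The provisions nearest to it are these:
   - Section 11.8 requires notification of a pregnancy in the subject or a partner, and follows that person. A recipient of donated sperm need be neither.
   - Section 11.8 adds that "any SAE occurring as an adverse pregnancy outcome post-study must be reported to the Medical Monitor". This duty arises only after an adverse outcome.
   - Section 11.3.1 has a parallel post-study duty, which begins "If the Investigator becomes aware of any SAEs that occur after the study period that are believed to be causally related". It depends on the investigator learning of the event.

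All of these concern what to do after an event. None prevents donation.

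**The case against.** The best answer is that this is a misplaced modifier: the sponsor surely meant all men, and any experienced site would read it so. Exclusion 18 also lets the Principal Investigator refuse any volunteer, including one who plans to donate. Consent pages were removed from the copy reviewed, and they may state the ban without condition. Subjects are housed in the unit from Day -1 to Day 14, so donation is not practical for the first two weeks. No passage describes a risk carried by semen or donated sperm. Affected men would have to be both outside the condition and willing to donate within the window, and nothing suggests that even one will be enrolled.

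Much of this stands, and it limits the weight of the point. It does not remove the point. If all men were meant, the criterion does not say so. Exclusion 18 is discretionary and does not mention donation. Consent wording, whatever it says, would not repair the stated criterion. The inpatient stay covers only a small part of a window that lasts at least 7 months.

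A reader might also infer that the contraception rules conflict more widely, because inclusion 4a demands a failure rate below 1% per year and sends the reader to Appendix 1, which is headed as a list of acceptable methods and includes a double barrier method. The documents do not support that as a finding. Inclusion 4a states its own standard, which binds whatever the appendix is called. No failure rate is given for any listed method, so singling out the double barrier entry would rest on outside knowledge. Nor does the entry "Abstinence from heterosexual intercourse" show that the protocol had abstinent men in mind: among the contraception criteria only 4a, which concerns women, cites that appendix. The point about inclusion 7 rests on its own wording.

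**Conclusion.** The point holds as a minor wording correction on reproductive safety. As written, inclusion 7 does not apply the sperm-donation ban to male subjects without pregnancy-risk sexual activity, while inclusion 6 applies the egg-donation ban to every woman, and nothing else in the protocol shown fills the gap.

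Its size cannot be put in numbers. The sex split is not stated, and neither is the share of men outside the condition or the likelihood that any would donate. The number affected is unknown and probably small. No endpoint, sample size or analysis is touched.

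The conclusion assumes that the criterion is applied as written and that the sponsor wants its own 7-month restriction to follow dosing. A reader might go further and infer that CD388 is known to be harmful through donated sperm. The protocol says only that risks in pregnancy are unknown, so that inference is not supported.

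**What to change.** In inclusion 7, in both Section 7.1 and the Synopsis, keep the double barrier requirement for men whose sexual activity risks pregnancy and end the sentence there. Then add a separate sentence with its own subject: All male subjects must "agree not to donate sperm during the study and for at least 7 months after the last dose of the study medication".

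Check the consent form and bring it into line if it carries the same condition. The cost is one sentence of protocol text and possibly one of consent text. No procedure, visit or analysis changes, and the only men newly asked for anything are those to whom the ban does not at present apply.
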